3.1 Primary Aim

The primary aim is to study the continuous pattern of vital parameters, collected over a long duration, within a sample cohort of consenting patients with SCD in order to determine how these relate to acute and chronic illnesses, as well as healthcare utilisation.

This will be through the creation of a unified data platform – comprising historical patient data, a full genetic background, and real-time patient data – through the incorporation of a wearable device into patient disease management.

Through this, the intended outcome will be improved quality and duration of life in patients.

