Similarly, patients living with SCD are faced with an increasing risk of chronic complications and organ damage (e.g. renal failure, pulmonary hypertension) as they age, and the need to understand the currently uncertain cause underlying the progression to these states in certain patients will be essential in detecting, predicting and preventing these complications in the future. Long term studies following large cohorts of patients through ongoing and in-depth data collection are currently severely lacking, clinicians as a result unable to definitively identify those patients at risk of advancing to these severe disease states or establish which interventions would provide the best outcomes for these patients, based on their demographics, genetics, comorbidities and disease progression thus far. Although a number of studies have investigated the associated metrics linked to renal failure within their SCD patient cohorts, previous work having identified male gender, proteinuria, cardiovascular diseases, and transfusions as potential risk factors in acute renal failure, these findings are based solely upon databases comprised of inpatient services, inpatient admissions, outpatient services, and prescription drug claims^{xi}. While certainly an important part of establishing the potential causes or triggers of renal failure, such data again looks only at the patient profile at their most severe points in their pathway, and subsequently miss the complex network of additional factors which may cause the gradual progression to renal failure over the years.

These frequently flagged issues in providing the best standards of care to their patients demonstrate the importance of a better understanding of the specific metrics involved, correlating the factors that have historically shown a strong likelihood of progression to a severe disease state, and matching patients with others of a similar profile in terms of areas such as age, gender, comorbidities and genotype who may be at a more advanced stage of their disease, in order to

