see which treatment options have offered the best outcomes. Closer monitoring of patients beyond this on a day-to-day basis provides the ability to change treatment pathways or provide interventions in a preventative manner, identifying potential adverse events or outcomes before the point of no return. The aim of this study is therefore to build a digital patient profile which will help to support the study of SCD's natural history, produce risk stratifications, predict long-term impacts, and create a correlation matrix of metrics signalling, for example, a potential crisis or the early stages of progression to renal failure, flagging issues earlier in the cycle for faster interventions, or even raising the alarm before a crisis is triggered. Patients will have full visibility of their data and the resulting insights to manage their own care more effectively and pre-emptively, with support from clinicians through earlier detection of adverse events.

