The main objective of this project is to establish a digital patient profile to identify and monitor for the key risk factors or triggers around SCD pathologies, such as VOC and organ damage, as well as the best treatment options for these patients. Furthermore, the resulting unified platform will help to collate the necessary information needed to empower patients in managing their own care, and access specialist clinician advice as and when they need it.

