4.5.2 Digital Data Platform and Wearables Pilot

Patients who enrol onto the pilot trial, either as a follow on from the patient focus groups or through recruitment via the Sickle Cell Society, London North West University Healthcare NHS Trust, or Barts Health NHS Trust, will be able to use either their own existing device or will be provided with a comparable market available smartwatch by the study. Data points, as summarised in Section 4.3, will be collected in an automated fashion on an ongoing basis, before transmission to a secure cloud database. This provides a novel approach to the monitoring of SCD that forgoes the need for patients to manually record information themselves and provides the potential for a larger patient cohort through remote monitoring, collecting a greater wealth of more in-depth, real-time and longitudinal data from patients during their daily lives. This supports a higher degree of compliance through decreased intrusion and an improved quality of data through improved objectivity and the elimination of retrospective recall. Furthermore, the utilisation of a wearable device provides the establishing of a baseline identified by 24/7 monitoring of data collection, providing a precise comparison for any patterns and changes over time to inform improved treatment pathways.

Patients will be set up with an electronic account and access to the digital platform through which their personal data can be accessed and visualised, and any additional metrics – such as body weight, dietary intake, emotional wellbeing, and additional medication consumption – can be manually input by the patient themselves as desired.

5. Project Plan

As part of the process of engaging patients prior to the full study and technology pilot trial, the project entails a series of initial pre-study patient focus groups over a 2-month period, in order to gather the relevant insights to ensure the study design, steps and outcomes are curated around a patient-centric outlook. Our intended timetable is as follows:

Project Stage	2 months	3 months	12 months				1 month
1 Pre-Study Focus Groups Engaging patients in study development prior to initiation of the full wearable pilot							
2 Pilot Study Enrolment Patients recruited to participate in the pilot through pre-study focus groups, the Sickle Cell Society & participating trusts							
3 Wearables Pilot Study Trialling of the live wearable and digital platform with patients, data collection, and analysis							

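### The aims extend to chronic illness and prediction of organ damage, but the timetable gives about 12 months of wearable data, too little to predict damage that takes years, and existing disease is not separated from new

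*Protocol*

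**What the plan says.** Section 3.1 of the Protocol sets the primary aim: to "study the continuous pattern of vital parameters, collected over a long duration, within a sample cohort of consenting patients with SCD". The length of the collection period is not given as a number. The stated purpose is to "determine how these relate to acute and chronic illnesses, as well as healthcare utilisation".

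Other sections go further than association. The main objective in Section 3 is a digital profile to "identify and monitor for the key risk factors or triggers around SCD pathologies, such as VOC and organ damage". Section 2.1 says the profile will help to "produce risk stratifications, predict long-term impacts, and create a correlation matrix of metrics signalling", with an oncoming crisis or early renal progression as the examples. The same section criticises studies built on inpatient and claims data because they "miss the complex network of additional factors which may cause the gradual progression to renal failure over the years", and it regrets the lack of long-term cohorts.

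Section 5 contains the only timetable. Its columns are 2, 3, 12 and 1 months, and it has four stages. Stage 3, the wearables pilot, is described as "Trialling of the live wearable and digital platform with patients, data collection, and analysis". Stage 4 is a feedback round with participants. No later observation is scheduled, although Sections 2.4 and 4 describe the project as ongoing.

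Section 8 brings the record data (Section 4.2) and the wearable data (Section 4.3) into one stepwise regression. It lists comorbidities and wearable data among the variables to be correlated, and it makes disease progression during the study an additional focus. The associations found then inform the predictive algorithms. Nothing distinguishes a complication present at enrolment from one that arises afterwards.

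**The concern.** The aims and the schedule run on different time scales. By the Protocol's own account, renal progression takes years; the scheduled wearable series lasts about one. The linked records can supply earlier diagnoses, but not earlier continuous vital signs, so the wearable exposure begins at enrolment.

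Eligibility is open to any patient with SCD from age 5 (Section 6.1), so patients who already have organ damage will be enrolled. If few new complications arise, the association between vital signs and chronic illness will be driven by those patients. In them the vital signs were measured after the damage and may be a consequence of it. Such an association cannot show what precedes damage. Under Section 8 it could nevertheless pass into the predictive algorithms and their treatment-pathway suggestions, and Section 2.1 gives patients full sight of the resulting insights. An association of unknown temporal order could then be read as an early warning.

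**Working it through.** **Inputs from the Protocol.** Sample size 300, as 2% of a UK population of 12,500 to 15,000 (Section 4.1); timetable of 2, 3, 12 and 1 months (Section 5); significance at p below 0.05 (Section 8).

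**Assumptions.** The Protocol gives no incidence, effect size or power. I assume 0.5 to 10 first chronic complications per 100 patient-years, hazard ratios of 2 and 3 for one wearable marker split 50/50, a two-sided test, 80% power and no losses.

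**1. The plan's own figures.** 0.02 × 15,000 = 300, so the sample size reproduces at the upper population figure; 0.02 × 12,500 = 250. The size has no power basis. The timetable sums to 2 + 3 + 12 + 1 = 18 months.

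**2. Wearable follow-up.** The bars of the timetable are not visible, so stages are matched to columns by order. The text of Section 5 gives the pre-study focus groups 2 months, which fits the first column. On that reading the pilot is the 12-month stage, giving at most about 300 × 1 = 300 patient-years.

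**3. Events needed.** Schoenfeld: d = (1.960 + 0.842)² / [0.25 × (ln HR)²].
- HR 2: 7.849 / (0.25 × 0.4805) ≈ 65.3, so 66 events.
- HR 3: 7.849 / (0.25 × 1.2069) ≈ 26.01, so 27 events.

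**4. Events expected and power.** Expected first events = 300 × (1 − e^(−rate)); chance of none = e^(−300 × rate); power = Φ(√(0.25d) × ln HR − 1.960); years to 66 events = 66 / (300 × rate).

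| Assumed rate per year | New cases in 12 months | Chance of none | Power, HR 2 | Power, HR 3 | Years to 66 events |
|---|---|---|---|---|---|
| 0.5% | 1.5 | 22.3% | 6.2% | 9.9% | 44 |
| 1% | 3.0 | 5.0% | 8.7% | 15.6% | 22 |
| 2% | 5.9 | 0.2% | 13.2% | 26.7% | 11 |
| 5% | 14.6 | <0.1% | 26.3% | 55.6% | 4.4 |
| 10% | 28.5 | <0.1% | 45.7% | 83.5% | 2.2 |

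At 3 per 100 patient-years the count is about 300 × 0.03 = 9.

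**5. Does the result depend on the missing bars?** No. If every patient were observed for all 18 months, the highest assumed rate would give at most 300 × 1.5 × 0.10 = 45 events, still below 66.

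**6. Acute events for comparison.** At an assumed 0.5 to 2 per patient-year, 300 × (1 − e^(−0.5)) = 118 to 300 × (1 − e^(−2)) = 259 patients have at least one event in 12 months. Power at HR 2 is at least 96%.

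**The case against.** The strongest reply is that Section 3.1 asks only how vital signs relate to chronic illness, and a cross-sectional association meets that wording. The renal example stands in the rationale and is not listed as a 12-month output. The digital profile also draws on years of hospital and GP records and on matching patients with others at a more advanced stage, a route that 12 months does not limit. Section 8 calls the study exploratory and sends significant results to further study. A separate SAP, not shown here, might also distinguish existing from new disease.

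Much of this stands, and it rules out several stronger readings that a reader might infer:

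- *Only acute events can be followed prospectively.* Not so. Healthcare use can be followed, pathology and radiology results are collected (Section 4), and some new chronic events would be recorded.
- *Half of the primary aim is lost.* Chronic illness is one of three named targets.
- *Cause and effect will be reversed.* Existing cases leave temporal order undetermined; reversal is possible, not shown.
- *Collection stops at month 12.* The 12 months are inferred from column order, and no passage gives a stopping date. What can be said is that no later follow-up is scheduled.
- *Consent omits longer linkage.* The consent pages were not available, so this cannot be asserted.

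The reply does not remove the core. The historical records hold no earlier wearable series; any history on patients' own devices is not described as a data source. The match between aim and timetable belongs to the Protocol, not the SAP. Calling the project ongoing fixes no follow-up, and the expansion mentioned in Section 6 is to more treatment centres, not longer observation.

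**Conclusion.** The point holds in this form: the scheduled wearable data suit prospective study of acute events and healthcare use, but are unlikely to support reliable prediction of new organ damage. Chronic-illness associations from the pilot would come mostly from complications already present.

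At 0.5 to 3 new complications per 100 patient-years, about 1.5 to 9 cases are expected; at 10 per 100, about 29, with 46% power for a hazard ratio of 2. Only at that highest rate, and for a hazard ratio as large as 3, does power pass 80%, and that is for a single marker chosen in advance, not for stepwise selection among many. The rates, hazard ratios and complete follow-up are my assumptions. The Protocol also gives no prevalence of organ damage, so the predominance of existing cases is a judgement from the open eligibility and the low expected count of new ones. The mismatch between a process of years and an 18-month timetable needs none of these assumptions.

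**What to change.** - **Sections 3.1 and 8:** name acute events and healthcare use as the prospective outcomes of the pilot. Analyse and report complications present at enrolment separately from new ones. Label the former cross-sectional and not predictive, and do not pass them to the predictive algorithms as signals of early progression. State that prediction of organ damage is a goal for later follow-up, not a pilot result.
- **Section 5:** state that the EMR and HES linkage already planned continues for a fixed number of years after the pilot, with consent to cover it if it does not already. The stored wearable data can then be tested against complications that arise later.

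The cost is mainly wording; no extra patients or visits are needed. The longer linkage needs some governance work, because Section 9.1 requires clearly defined purposes and Section 9.4 requires explicit authorisation for access to trust data. The pilot would also claim less about chronic illness. Any consent change is best made before enrolment, since later re-consent would lose patients.

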3.2 Secondary Aim

A secondary aim is to further develop the features and usability of the data platform and wearable device through a patient lens, in an ancillary study with patient focus groups around 3 key research areas: SCD's impact on psychological wellbeing, the usefulness of wearables in day-to-day patient life, and concerns around consenting to data sharing.

4. Project Design

[figure not shown]
The project will be a combination of focus groups and data collection. This will be an ongoing, data-driven project, revolving around the collation of episodic and live data points including admission, diagnostic, pathology, radiology, primary care, pharmacy, physiotherapy, Hospital Episode Statistics (HES), Open Data, clinical data points, and the incorporation of live wearable device data. Cultivation of the most relevant data points in the context of SCD has been ongoing with the support of expert clinicians in the field, and will be further developed through the input of patients themselves during a series of patient focus groups, in order to establish what the most important factors are to SCD care through a patient-lens. Wearable devices will be provided to patients who do not already own one, in support of the unified digital data platform, within a pilot study with consenting patients who choose to register following these patient focus groups, as well as those who have enrolled through the Sickle Cell Society and from patient cohorts at treatment centres such as London North West University Healthcare NHS Trust and Barts Health NHS Trust. The project's development will further be supported through the inclusion of a number of focus groups between specialist doctors and nurses, as well as healthcare managers, public health officials and commissioners.

4.1 Sample Size

There is an estimated 12,500-15,000 people living with SCD in the UK^{xvii}. Our patient sample size is based upon an estimated minimum proportion of the total population of patients with SCD we aim to enrol onto the digital platform and wearables pilot study, assuming not all patients will be reached by the initial programme launch through the Sickle Cell Society and partnering trusts, and that of those who are, not all will provide consent or be interested in participating. As such, our starting goal is to recruit 2% of the total UK SCD patient population, at 300 patients.

4.2 Data Sources, Access and Flow

From the starting point of sources including hospital Electronic Medical Records (EMRs), open data, and Hospital Episode Statistics (HES), the data platform will integrate written medical and primary care records from GPs, structured and unstructured EMIS/TPP records, as well as genetic information through external organisations such as 23andMe, following full patient consent. With additional wearables collected data (Section 4.3), these sources will be combined within a specialised SCD unified data platform to allow the application of a set of advanced algorithms, providing granular analysis of key patient metrics.

4.3 Wearable & App Data Points

Following specification of the most crucial metrics, live data points will be integrated into the unified data platform directly from patients through the use of wearables and ongoing monitoring of factors, or through optional manual input of additional information, such as a pain scale of mood, through the platform's mobile app by patients. These include:

Metric	Rationale
Heart Rate	A fast heart rate is linked to anaemia and low blood O ₂ , stress, and panic attacks.
Blood O₂ Saturation	Low arterial blood oxygen saturation is common in SCD, and Obstructive Sleep Apnoea is also highly prevalent in patients with SCD.
Body Temperature	Raised or decreased temperatures are linked to crises, with low body temperatures known to trigger vasoconstriction. High temperatures can also be an indication of infection and in turn trigger crises.
Blood Pressure	Blood pressure is known to be lower in SC anaemia, with relative hypertension linked to an increased risk of stroke, pulmonary hypertension, renal dysfunction & death. This can also be used as an important indicator of stress.
ECG Abnormalities	ECG abnormalities are common in SCD & early identification / intervention can help to prevent serious cardiac events, e.g. Myocardial Infarction during VOC.
Sleep Cycles	Disrupted sleep cycles / patterns are linked to increased pain and periods of crisis.
Fitness & Activity	Low activity levels may be an indicator of the onset of a crisis, and certain exercises are linked to relieving pain.
Nutrition / Diet / Medications taken	Can be an important indicator of emotional wellbeing & pain levels, with disrupted eating patterns or loss of appetite potentially indicating periods of chronic pain or VOC.
Pain and Symptoms	Provides a direct monitor of patient wellbeing and will support correlation of metrics with symptoms of SCD pathologies.

4.4 Focus Groups

Part of this project will involve hosting a number of focus groups and collating the key learnings from these over a 12-month period. The purpose of these focus group studies revolves around incorporating the patient voice directly into the development of the unified SCD data platform and the introduction of a digital data platform and wearable device into care management. The goal of this is to assess how patients feel in the context of a 3-pronged programme: psychological wellbeing, wearables, and consent for data sharing over the SCD data platform. By gaining a deep level of insight around the specific needs of the patient, the aim is to fully incorporate the patient voice into future developments, ensuring all features are aligned to what will benefit patients day-to-day. An overview of the 3 research questions is given in the table below:

Focus / Objective	Key Questions

Psychological Wellbeing
 
To identify the psychological support needs of SCD patients and their families / carers.
	
Impact of SCD on psychological wellbeing and the support patients are currently receiving
 
 • How does SCD affect your daily living and quality of life? • How does SCD effect you emotionally? • What are your thoughts / feelings about SCD, and how do you cope with these? • What emotional support have you received, and what would be useful? • How could wearables be used to help monitor and manage your emotional wellbeing?

Devices/Wearables
 
To find out the likelihood of wearables adoption by SCD patients and the key features that would benefit patient care management.
	
Wearables, devices and capturing data
 
 • Do you currently use any wearables? If so, what type? • How often do you use it or any accompanying apps? • During a crisis, what are the key things you would want to monitor / track? • Are there any triggers or warning signs of an oncoming crisis that you have become aware of over the years? • What are the key features you would want to see in your wearable device? • Would you consider using anything requiring manual input during a crisis or solely automated monitoring?

Data platform & consent
 
To identify the key concerns around health data collection for SCD patients and the factors that would encourage consent.
	
Data and consent for data collection from GP practices, hospitals, wearables into the platform
 
 • What would your main concerns be around this form of data collection? • What would be the key factors in ensuring you feel comfortable with this?

Each focus group session will host discussion between 15-20 patients over a dedicated Zoom call, led by a clinician facilitator, and will be divided by age group:

- i. Parents with their effected children

- ii. Teenagers / adolescents, 13-18 years of age
- iii. Young adults, 19-25 years of age
- iv. Adults, 26-39 years of age
- v. Older adults, 40-64 years of age
- vi. Elderly, 65 years and over

4.5 Procedure

4.5.1 Focus Groups

Patients will be approached and enrolled onto the initial focus group programme with support from the Sickle Cell Society and specialists at London North West University Healthcare NHS Trust and Barts Health NHS Trust. Following the introduction to the purposes and structure of the focus groups, with details provided from which to request additional information, patients will be given adequate time prior to the planned commencement of the focus groups to decide if they wish to participate. All patients will receive the necessary consent forms and full confidentiality and data security will be ensured, with no patient identifiable data collected, shared or transmitted over the internet. Any information recorded, either through manual recording of responses throughout the session, through the pre-focus group survey or through the interactive focus group form (Section 6) will be anonymised and require the input of no identifiable data.

